4. ANALYSIS POPULATION

The following analysis population will be defined for this study:

Safety Population: The Safety Population will consist of all subjects who receive AR101 during ARC008. The Safety Population will be used for all analyses.

5. **PROTOCOL DEVIATIONS**

Any change, divergence, or departure from the study design or procedures constitutes a protocol deviation. All protocol deviations will be reported on a specific case report form (CRF) as follows:

- Inclusion Criteria
- Exclusion Criteria
- Received Incorrect Study Treatment
- Informed Consent Form (ICF)
- SAE Not Reported
- Visit Out Of Window
- Missed Study Visit
- Procedure Not Per Protocol
- Prohibited Concomitant Medication
- Lab Sample Missed
- Study Drug Compliance
- Other, Specify

These protocol deviations will be reviewed prior to database lock and their categorization as major or minor will be determined prior to database lock. All protocol deviations, both major and non-major, will be listed and included in the study report.

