7.1.2. Peanut-Specific and Peanut Component-Specific IgE and IgG4

In the summaries of peanut-specific and peanut component-specific IgE and IgG4 (Section 11.1), End of Up-Dosing, End of Initial Maintenance, and Extended Maintenance visits will be reassigned to a study visit based on the actual days relative to the start of Extended Maintenance using the visit windows identified in Table 2 below. According to schedules of events in the appendices of the protocol, subjects in Treatment Pathways 2 and 3 will have scheduled immunology blood sample collection at End of Up-Dosing and subjects in Treatment Pathways 2, 3, and 5 will have a scheduled collection at the End of Initial Maintenance. Subjects from all treatment pathways will also have scheduled blood sample collection after the first 12 months of extended maintenance treatment and yearly thereafter as well as at End of Treatment and Study Exit. Visit windows are therefore defined to capture all scheduled blood sample collection for each treatment pathway. Nominal visits will be used in the summary of End of Treatment and Study Exit visits.

For Treatment Pathways 1 and 4, the start of Extended Maintenance is defined as the date and time of first in-clinic or at home dose of treatment in ARC008. For Treatment Pathways 2, 3, and 5, the start of an Extended Maintenance is defined as the first visit labeled as an Extended Maintenance visit.

Treatment		Months Since Start of Extended Maintenance	
Pathway	Visit	Target Month	Window Interval
2, 3	End of Up-Dosing	-6	< 0
2, 3	End of Initial Maintenance	0	[0, 6)
5	End of Initial Maintenance	0	< 6
1, 4	Extended Maintenance: Month 12	12	[0, 18)
2, 3, 5	Extended Maintenance: Month 12	12	[6, 18)
All (1-5)	Extended Maintenance: Month 24	24	[18, 30)
All (1-5)	Extended Maintenance: Month 36	36	[30, 42)
All (1-5)	Extended Maintenance: Month 48	48	[42, 54)
All (1-5)	Extended Maintenance: Month 60	60	≥ 54

Table 2 Visit Windows for Analysis of Immunoglobulin Results

If more than one value is mapped to the same visit, the value collected closest to the target month will be considered for summarization. If two values collected on different days are mapped to the same scheduled visit and are equidistant from the target month, the earlier of the values will be considered. Nominal visits will be presented in the data listings of peanut-specific and peanut component-specific IgE and IgG4 results.

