7.2. DATA PRESENTATION

Individual subject data listings will be provided to support summary tables and serve as a data source. Unless otherwise noted, all electronic data capture (EDC) data collected in the clinical database for all enrolled subjects will be included in the data listings, including the derived study period flags and captured nominal visit labels. If a listing includes screen failures, they will be listed as such and sorted after all enrolled subjects.

Visits labelled as unscheduled will also be listed.

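### SAP Table 2, Pathways 2 and 3: month 0 as written does not fit the targets of -6 and 0, and on the protocol's visit names no on-schedule sample falls in the End of Initial Maintenance window

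*SAP*

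**What the plan says.** SAP 7.1.2 covers the immunoglobulin summaries. It states that "End of Up-Dosing, End of Initial Maintenance, and Extended Maintenance visits will be reassigned to a study visit" according to time since the start of Extended Maintenance. For Pathways 2, 3 and 5, "the start of an Extended Maintenance is defined as the first visit labeled as an Extended Maintenance visit".

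For Pathways 2 and 3, Table 2 gives:
- End of Up-Dosing: target -6, window < 0
- End of Initial Maintenance: target 0, window [0, 6)
- Month 12: target 12, window [6, 18), followed by the later annual rows

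The SAP notes that "subjects in Treatment Pathways 2 and 3 will have scheduled immunology blood sample collection at End of Up-Dosing" and that Pathways 2, 3 and 5 have a further draw at the end of Initial Maintenance. It concludes: "Visit windows are therefore defined to capture all scheduled blood sample collection for each treatment pathway". When several values share a window, "the value collected closest to the target month will be considered for summarization".

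Protocol 7.2.4 and 7.3.5 call the first Extended Maintenance visit Month 3 (± 2 weeks) and schedule immunology blood in that period at annual visits only. The Week 24 draw is listed under Initial Maintenance (Protocol 7.2.3.2 and 7.3.4.2).

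**The concern.** The windows depend on which visit is month 0. Read with the protocol's visit names, the rule puts month 0 about three months after Week 24. The targets assume it lies at Week 24. Both pre-Extended-Maintenance samples then compete for the End of Up-Dosing row, and nothing scheduled falls in the End of Initial Maintenance row.

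SAP 11.1 summarizes immunoglobulins by time point for Pathways 1-3 together. Pathway 1 has neither of these rows in Table 2, so it cannot fill the gap. The result at 24 weeks of 300 mg maintenance would be missing from the table. Some values reported as End of Up-Dosing could also have been drawn after those 24 weeks.

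A second problem does not depend on the label. A subject who never has an Extended Maintenance visit has no month 0, and Table 2 gives no fallback.

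**Working it through.** **Inputs**
- One month = 365.25/12 = 30.4375 days (SAP 7.4).
- End of Up-Dosing to Week 24: 168 days nominal; Week 24 lateness w within ± 7 days (Protocol 7.2.3, 7.3.4).
- Week 24 to Month 3: 3 × 30.4375 = 91.3125 days nominal; Month 3 lateness d within ± 14 days (Protocol 7.2.4, 7.3.5).
- Assumption: Month 3 is counted from the actual Week 24 date, because Protocol 3.2.4 has subjects enter Extended Maintenance at Week 24.

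**The plan's own targets.** With month 0 at Week 24, End of Up-Dosing is at -168/30.4375 = -5.52 and Week 24 at 0.00. This matches -6 and 0, and each sample falls in its intended window.

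**Month 0 at Month 3**
- Week 24 = -(91.3125 + d)/30.4375 = -3.00, range -105.3125/30.4375 = -3.46 to -77.3125/30.4375 = -2.54.
- End of Up-Dosing = -(91.3125 + d + 168 + w)/30.4375 = -8.52, range -280.3125/30.4375 = -9.21 to -238.3125/30.4375 = -7.83.

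| Sample | Month 0 at Week 24 | Month 0 at Month 3 | Window under Month 3 |
|---|---|---|---|
| End of Up-Dosing | -5.52 | -8.52 | < 0 |
| Week 24 | 0.00 | -3.00 | < 0 |
| Month 12 | 12 | 9 (8.08 to 9.92) | [6, 18) |
| Months 24, 36, 48, 60 | 24, 36, 48, 60 | 21, 33, 45, 57 | each in its own row |

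No on-schedule sample falls in [0, 6). End of Treatment and Study Exit samples cannot fill it, because they are not windowed.

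**Which value the End of Up-Dosing row keeps.** On schedule, the distances to -6 are 8.52 - 6 = 2.52 for End of Up-Dosing and 6 - 3.00 = 3.00 for Week 24. The true End of Up-Dosing value is kept and Week 24 is dropped.

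In days, with the target 6 × 30.4375 = 182.625 days before month 0, the distances are:
- Week 24: 182.625 - 91.3125 - d = 91.3125 - d
- End of Up-Dosing: 91.3125 + d + 168 + w - 182.625 = 76.6875 + d + w

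Week 24 is closer when d > 7.3125 - w/2. With Week 24 on time (w = 0), that means Month 3 is 8 or more whole days late, which is inside the ± 14-day tolerance. At w = +7 the switch comes at day 4, and at w = -7 at day 11.

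**No competing sample.** Some Pathway 2 subjects begin ARC008 in Initial Maintenance (Protocol 3.2.4, 7.2.3) and have no ARC008 End of Up-Dosing draw. Week 24 is then their only scheduled value in the < 0 window, so it is reported as End of Up-Dosing even with every visit on time.

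**No month 0.** A subject can stop after the End of Up-Dosing draw and before any Extended Maintenance visit. That interval is 168/30.4375 = 5.52 months if Week 24 carries the label, and 259.3125/30.4375 = 8.52 months if Month 3 is first. In either case the sample cannot be placed in Table 2.

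**The case against.** The strongest reply is that the anchor is a database label, and the labels are not in the supplied text. Week 24 may carry an Extended Maintenance label. The targets of -6 and 0 point that way. So does Protocol 3.2.4, under which subjects enter Extended Maintenance at Week 24. Week 24 is also followed by the same 6-to-7-week telephone contact as Extended Maintenance visits, which is not listed after Weeks 8 and 16. If the label is there, every on-schedule sample falls in its intended row. This stands as a possibility, but Protocol 7.2.4 and 7.3.5 name Month 3 as the first visit of the period. The separate tracking documents mentioned in SAP 7.7 might also have dealt with this; they were not available to check.

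Two stronger readings are tempting but not supported:
- **The End of Up-Dosing row is generally contaminated by Week 24 values.** On schedule it is not, because the closest-to-target rule keeps the right value. Replacement needs a late Month 3 or an absent End of Up-Dosing sample.
- **The annual rows are shifted by a year.** With Month 3 as month 0 they are correct. A one-row shift needs Months 3 and 6 both missed, so that Month 9 is first and Month 24 falls at 24 - 9 = 15. SAP Section 5 has a deviation category "Missed Study Visit" but gives no frequency, and SAP Section 1 says visits continued remotely during the pandemic.

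It is also fair to say that the consequence is small. These are descriptive rows of an exploratory endpoint, and listings keep nominal visits.

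**Conclusion.** Wrong as written, and minor. The stated anchor, read with the protocol's visit names, gives -8.52 and -3.00 where Table 2 has targets of -6 and 0. It leaves the End of Initial Maintenance row empty or nearly so for Pathways 2 and 3. This part is conditional on Week 24 not carrying an Extended Maintenance label, and on nominal spacing of 168 and 91.3125 days.

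The gap for subjects without a month 0 is unconditional. It contradicts the SAP's statement that the windows capture every scheduled sample.

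The effect is confined to by-time-point immunoglobulin rows for Pathways 1-3. Listings, End of Treatment, Study Exit and the change to Study Exit are unaffected. The row overlap does not arise in Pathway 5, whose End of Initial Maintenance window is < 6. The documents give no count of affected subjects, so the number of lost or misplaced values cannot be estimated.

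**What to change.** First check which visit label set month 0. Then, for Pathways 2 and 3, assign the End of Up-Dosing and End of Initial Maintenance rows by nominal visit. The same section already does this elsewhere: "Nominal visits will be used in the summary of End of Treatment and Study Exit visits". The labels are available, since SAP 7.2 has the listings "including the derived study period flags and captured nominal visit labels". This restores the Week 24 row, stops Week 24 values entering the End of Up-Dosing row, and gives a row to samples from subjects without a month 0.

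Leave the annual windows and their anchor unchanged. Tables 1 and 3 use the same anchor, and moving it for immunoglobulins alone could assign one annual visit differently across food challenge, skin prick test and immunoglobulin summaries.

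State in the CSR which visit label set month 0. SAP 1.1 says Version 2 was made after database lock and is restricted to Appendix A, so the change should be reported as post-lock. If Week 24 does carry the label, that statement and a rule for subjects without a month 0 are enough.

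The cost is the label check, one sentence, and a rerun of one exploratory summary.

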7.1.3. Skin Prick Test

In the summaries of skin prick test results (Section 11.2), End of Up-Dosing, End of Initial Maintenance, and Extended Maintenance visits will be reassigned to a study visit based on the actual days relative to the start of Extended Maintenance using the visit windows identified in Table 3 below. According to schedules of events in the appendices of the protocol, subjects in Treatment Pathways 2 and 3 will have scheduled skin prick tests at End of Up-Dosing and subjects in Treatment Pathway 5 will have a scheduled test at the End of Initial Maintenance. Subjects from all treatment pathways will also have scheduled skin prick tests after the first 12 months of extended maintenance treatment and yearly thereafter as well as at End of Treatment and Study Exit. Visit windows are therefore defined to capture all scheduled skin prick tests for each treatment pathway. Nominal visits will be used in the summary of End of Treatment and Study Exit visits.

For Treatment Pathways 1 and 4, the start of Extended Maintenance is defined as the date and time of first in-clinic or at home dose of treatment in ARC008. For Treatment Pathways 2, 3, and 5, the start of an Extended Maintenance is defined as the first visit labeled as an Extended Maintenance visit.

Treatment		Months Since Start of Extended Maintenance	
Pathway	Visit	Target Month	Window Interval
2, 3	End of Up-Dosing	-6	< 0
5	End of Initial Maintenance	0	< 6
1-4	Extended Maintenance: Month 12	12	[0, 18)
5	Extended Maintenance: Month 12	12	[6,18)
All (1-5)	Extended Maintenance: Month 24	24	[18, 30)
All (1-5)	Extended Maintenance: Month 36	36	[30, 42)
All (1-5)	Extended Maintenance: Month 48	48	[42, 54)
All (1-5)	Extended Maintenance: Month 60	60	≥ 54

Table 3 Visit Windows for Skin Prick Test Results

If more than one value is mapped to the same visit, the value collected closest to the target month will be considered for summarization. If two values collected on different days are mapped to the same scheduled visit and are equidistant from the target month, the earlier of the values will be considered. Nominal visits will be presented in the data listings of skin prick test results.

7.2. DATA PRESENTATION

Individual subject data listings will be provided to support summary tables and serve as a data source. Unless otherwise noted, all electronic data capture (EDC) data collected in the clinical database for all enrolled subjects will be included in the data listings, including the derived study period flags and captured nominal visit labels. If a listing includes screen failures, they will be listed as such and sorted after all enrolled subjects.

Visits labelled as unscheduled will also be listed.

7.3. MAXIMUM TOLERATED CHALLENGE DOSE AT EACH FOOD CHALLENGE

The MTD for a food challenge is defined as the maximum single dose of peanut protein resulting in no more than mild symptoms and assessed by the investigator to have been tolerated (i.e., the subject did not experience any dose-limiting symptoms). Any symptom requiring treatment is inherently dose-limiting; thus, a dose during a food challenge cannot be considered "tolerated" if treatment was deemed necessary by the investigator.

7.4. DATA DERIVATIONS AND DEFINITIONS

The following definitions and derivations will be used throughout this study:

- Study Day is calculated as (assessment date date of first dose of AR101 in ARC008 + 1) for assessments and visits performed on or after the date of first dose of AR101 in ARC008, and (assessment date – date of first dose of AR101 in ARC008) for assessments and visits prior to the date of first dose of AR101 in ARC008. There will therefore be no Study Day 0.
- Baseline is defined as the last non-missing value prior to the first dose of AR101 in ARC008.
- Change from baseline is calculated as observed value after the first dose of AR101 in ARC008 baseline value.
- A duration expressed in months will be calculated by dividing the duration in days by (365.25 / 12).

• A duration expressed in years will be calculated by dividing the duration in days by 365.25.

The study periods are defined in Table 4 (used to create the study period flags) with the first and last dose dates for each study period being identified as follows:

Study Period	Treatment Pathways	First Dose Date	Last Dose Date
Initial Escalation	3 and 5	Date and time of first in-clinic dose at Initial Escalation Day 1	Date of latest in-clinic dose at Initial Escalation Day 1 or Day 2. Set the time to be 23:59 and 59 seconds on each of these respective days.
Up-Dosing	2	For subjects that do not undergo Repeat Up-Dosing: the date and time of first in-clinic or at home dose of treatment in ARC008 if prior to date of first Initial Maintenance Visit. For subjects that undergo Repeat Up- Dosing: the date repeat up-dosing (Treatment Pathway 2) was started.	Date of first in-clinic dose of 300 mg during the Up-Dosing period. For subjects who do not reach the 300 mg dose: the latest of the last in-clinic dose during the Up-Dosing period or the date of last dose at home. Set the time to be 23:59 and 59 seconds on the respective day.
	3 and 5	The day following the date of last in- clinic dose at Initial Escalation Day 2	Date of first in-clinic dose of 300 mg during the Up-Dosing period. For subjects who do not reach the 300 mg dose: the latest of the last in-clinic dose during the Up-Dosing period or the date of last dose at home. Set the time to be 23:59 and 59 seconds on the respective day.
Initial and Extended	1 and 4	Date and time of first in-clinic or at home dose of treatment in ARC008	Date of last dose of study product
Maintenance	2, 3, and 5	The day following the date of first in- clinic dose of 300 mg during the Up- Dosing period. For subjects who did not enter the Up-Dosing period: the date of first Initial Maintenance Visit.	Date of last dose of study product
Follow-Up Observation	All (1-5)	The day following the date of last dose of study product	Date of Study Exit visit. For subjects without a date of Study Exit visit: the date of study completion.
Overall	All (1-5)	Date and time of first in-clinic or at home dose of treatment in ARC008	Date of Study Exit visit. For subjects without a date of Study Exit visit: the date of study completion.

Table 4Study Period Definitions

- The active treatment period is defined as the time period beginning with the date and time of the first dose of study product and ending with the date and time of the last dose of study product.
- Duration of active treatment period (days) for AR101 is calculated as the date of last dose minus the date of first dose of AR101 plus 1.

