2.4.1. Treatment Pathways

Because the dosing regimens and procedures in the parent studies are not uniform, subjects will receive AR101 in 1 of 5 treatment pathways in ARC008:

- Treatment Pathway 1 is for subjects who received and tolerated AR101 in a daily or non-daily regimen in the parent study (except study ARC005). These subjects will undergo a Screening/Baseline visit, and eligible subjects will enter the Extended Maintenance Period. Subjects entering ARC008 on a dose > 300 mg once daily (QD) will switch to 300 mg QD on the first day of the Extended Maintenance Period. Subjects from parent study ARC004 on non-daily regimens who did not tolerate 600 mg peanut protein (1043 mg peanut protein cumulative dose) at the ARC004 Exit double-blind, placebo-controlled food challenge (DBPCFC) will switch to 300 mg QD on the first day of the Extended Maintenance Period. Subjects receiving non-daily AR101 regimens in parent study ARC004 who tolerated 600 mg peanut protein (1043 mg peanut protein cumulative dose) at the ARC004 Exit DBPCFC will continue the non-daily AR101 regimen in the Extended Maintenance Period.
- Treatment Pathway 2 is for the following subjects:
 - Subjects who did not complete their AR101 dosing regimen (eg, up-dosing, maintenance) in an eligible parent study (except study ARC005).
 - Subjects from parent study ARC004, or any future clinical study identifying ARC008 as a follow-on study, who received a non-daily AR101 dosing regimen and who did not tolerate this regimen.
 - Subjects from ARC004 who missed or withheld their non-daily AR101 dose for > 3 days, and subjects who received a non-daily AR101 dosing regimen and tolerated less than the 300 mg single dose of peanut protein (443 mg cumulative) at the ARC004 Exit DBPCFC, if continued treatment with AR101 was determined to be safe per investigator judgment and after discussion with the medical monitor.

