Subjects who did not complete their AR101 dosing regimen in an eligible parent study will have a Screening/Baseline visit and continue the regimen in ARC008, proceeding through the applicable study periods until the End of Treatment visit. Subjects who enter ARC008 soon after completing the ARC004 Early Discontinuation visit will have a Screening/Baseline visit, and eligible subjects will start the Repeat Up-Dosing Period at a dose of 80, 120, or 160 mg QD (a decrease in AR101 dose of approximately 50% to 75%) at the discretion of the investigator. These subjects will then proceed sequentially through the Initial Maintenance Period and Extended Maintenance Period. Subjects who complete the Repeat Up-

> Dosing Period or who tolerate AR101 300 mg QD for 2 weeks in ARC004 will have a Screening/Baseline visit in ARC008 and then proceed to the Initial Maintenance Period. Subjects who complete both the Repeat Up-Dosing and Initial Maintenance Periods or receive AR101 300 mg QD for at least 24 weeks in ARC004 will have a Screening/Baseline visit in ARC008 and then proceed to the Extended Maintenance Period. In addition, ARC004 subjects who tolerated the non-daily regimen in ARC004 but who subsequently do not tolerate the non-daily regimen after entering ARC008 Treatment Pathway 1 may switch to Treatment Pathway 2 and start the Repeat Up-Dosing Period at investigator discretion.

- Treatment Pathway 3 is for subjects who received placebo in the parent study (except study ARC005). These subjects will undergo a Screening/Baseline visit, and eligible subjects will start the Initial Escalation Period with a dose of 0.5 mg. Subjects will then proceed sequentially through the Up-Dosing Period, Initial Maintenance Period, and Extended Maintenance Period.
- Treatment Pathway 4 is for subjects who received AR101 and tolerated the 300 mg/day dose for at least 2 consecutive weeks before the exit DBPCFC in parent study ARC005. These subjects will have a Screening/Baseline visit, and eligible subjects will start the Extended Maintenance Period.
- Treatment Pathway 5 is for subjects who received placebo in parent study ARC005. These subjects will have a Screening/Baseline visit, and eligible subjects will start the Initial Escalation Period at a dose of 0.5 mg. Subjects will then proceed sequentially through the Up-Dosing Period, Initial Maintenance Period, and Extended Maintenance Period.

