6.3. SUBGROUP ANALYSES

The overall summary of treatment-emergent adverse events (TEAEs) and treatmentemergent serious adverse events (TESAEs) (Section 9.1) and the summary of rescue medications (Section 9.12) will be repeated for the following subgroups:

- Treatment Pathways 1-3
- Treatment Pathways 4-5
- Daily dosing regimen
- Non-daily dosing regimen

Daily and non-daily dosing regimen subgroups are based on the initial regimen assigned in ARC008.

The overall summary of treatment-emergent AEs of interest (AEIs) and treatmentemergent serious AEIs will also be summarized separately for Treatment Pathways 1-3 and 4-5.

Immunoglobulin values will also be summarized separately for Treatment Pathways 1-3, 4, and 5.

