11.2. SKIN PRICK TEST

SPTs will be conducted at the visits indicated in the schedules of events in the appendices of the protocol. Results from the SPT will be listed by treatment pathway, subject ID, and visit, including test date and time, and measurements (in mm) of the following: peanut wheal (long axis), peanut wheal (short axis), saline wheal (long axis), saline wheal (short axis), histamine wheal (long axis), and histamine wheal (short axis).

A derived mean wheal diameter score will be calculated as the average of the long and short axis from the peanut wheal minus the average of the long and short axis from the saline wheal. Summary statistics for the derived SPT mean wheal diameter will be presented at each visit, for change from baseline to End of Treatment, and for change from baseline to Study Exit visit by years of total AR101 exposure including parent studies and overall.

11.3. TEST FOR RESPIRATORY AND ASTHMA CONTROL IN KIDS (TRACK) AND ECZEMA AREA AND SEVERITY INDEX (EASI)

TRACK and EASI scores are measured as indicated in the schedules of events in the appendices of the protocol.

TRACK

In Treatment Pathways 4 and 5, asthma control in subjects aged 1 to < 5 years with preexisting asthma will be assessed using TRACK scores and by the incidence of asthma rescue medication use. Subjects who turn age 5 years during the study or who are aged \geq 5 years at enrollment in Treatment Pathways 4 and 5 will be administered the C-ACT questionnaire instead of the TRACK questionnaire.

The TRACK questionnaire will be administered at the visits indicated in the schedules of events in the appendices of the protocol. The parent/caregiver is to complete the TRACK, a 5-item standardized questionnaire used to evaluate respiratory and asthma control in children aged < 5 years with symptoms consistent with asthma (Zeiger, 2011). Each item is scored on a 5-point scale from 0 (4 or more times a week) to 20 (not at all). Higher scores indicate better respiratory and asthma control.

EASI

For subjects with pre-existing eczema or atopic dermatitis in Treatment Pathways 4 and 5, the severity of clinical signs of eczema or atopic dermatitis will be assessed using the EASI scoring system. Higher scores indicate greater severity of eczema or atopic dermatitis.

A listing of the results from the TRACK and EASI questionnaires will be provided, sorted by treatment pathway, subject ID, and visit.

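### Skin prick test change is measured from ARC008 entry but tabulated by total AR101 exposure with pathways pooled, and the layout of the immunoglobulin change summary is not stated

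*SAP*

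**What the plan says.** SAP 7.4 sets one baseline for every subject: "Baseline is defined as the last non-missing value prior to the first dose of AR101 in ARC008".

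SAP 2.4.1 shows what that value represents in each pathway:

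- Pathway 1 "is for subjects who received and tolerated AR101 in a daily or non-daily regimen in the parent study (except study ARC005"), so baseline is on treatment.
- Pathway 2 includes "Subjects who did not complete their AR101 dosing regimen (eg, up-dosing, maintenance) in an eligible parent study (except study ARC005") and ARC004 subjects who had trouble with a non-daily regimen. Baseline is again on treatment.
- Pathway 3 "is for subjects who received placebo in the parent study (except study ARC005"), so baseline is pre-treatment.
- Pathway 4 "is for subjects who received AR101 and tolerated the 300 mg/day dose for at least 2 consecutive weeks" in ARC005, so baseline is on treatment.
- Pathway 5 "is for subjects who received placebo in parent study ARC005", so baseline is pre-treatment.

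For SPT, SAP 11.2 plans summaries of mean wheal diameter at each visit, of change to End of Treatment, and of "change from baseline to Study Exit visit by years of total AR101 exposure including parent studies and overall". It gives no pathway split, and SAP 6.1 combines all pathways into one AR101 group as the general rule.

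For immunoglobulins, SAP 6.3 says "Immunoglobulin values will also be summarized separately for Treatment Pathways 1-3, 4, and 5". SAP 11.1 attaches that split, and the total-exposure strata, to the summary statistics by time point. A separate sentence in 11.1 covers change to Study Exit. It gives the log10 scale but names neither exposure strata nor a pathway split.

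**The concern.** The change and the row that contains it run on different clocks. The change starts at entry to ARC008. The exposure label starts at the first AR101 dose in any study. The two agree for a former placebo subject. For a subject already treated, part of the labelled exposure lies before baseline, and so does any effect on wheal size that occurred then.

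Pooling adds a second problem. One mean then combines changes from pre-treatment values with changes from values obtained after a year or more of AR101. The proportion of each kind can differ between exposure rows, so a trend or plateau across rows could reflect who is in each row and not the course of response.

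Within this SAP these are prominent tables. Section 13 drops the change summaries for PEF, ACT/C-ACT, TNSS, tolerated dose, FAQLQ/FAIM, FAQL-PB, TRACK and EASI. SPT and immunoglobulins are the change endpoints still summarized, and they serve the exploratory objective on immunologic effects of longer-term administration.

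**Working it through.** The plan states no sample size, effect size or expected change for these endpoints, so there is no figure of its own to reproduce. The check compares the time covered by the change with the exposure that labels the row.

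**Formula.** Treated time covered by change = total AR101 exposure − AR101 exposure before the ARC008 baseline. Weeks convert to years by 7/365.25. The figures below run to End of Treatment. Change to Study Exit adds roughly 12 months after the last dose in every pathway, which does not alter the comparison.

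**Inputs.**

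- End of Treatment comes at about 3 years in total for ARC005 subjects and about 5 years for most others (SAP 2.4.2.6). Some US subjects may stop sooner.
- ARC005 treatment lasts about 12 months (protocol 1.2.5).
- ARC003 maintenance lasts about 24 weeks. ARC004 lasts 28 to 84 weeks for those given AR101 in ARC003 (protocol 1.2.2).
- Up-dosing lasts 22 to 52 weeks in ARC008 Pathway 3 (protocol 3.2.3.2). That ARC003 used the same range is an assumption.

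**ARC005 subjects, 3-year total.**

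- Pathway 5: 3 − 0 = 3 of 3 years.
- Pathway 4: 3 − 1 = about 2 of 3 years.

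**Other subjects, 5-year total.**

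- Pathway 3: 5 − 0 = 5 of 5 years.
- AR101 in both ARC003 and ARC004, shortest: 22 + 24 + 28 = 74 weeks = 1.42 years before baseline. Change covers 5 − 1.42 = 3.58 years (72%).
- AR101 in both ARC003 and ARC004, longest: 52 + 24 + 84 = 160 weeks = 3.07 years before baseline. Change covers 5 − 3.07 = 1.93 years (39%).

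**Shift of mix across rows.** Subjects from that last route enter with at least 1.42 years of AR101, so they cannot appear in a row for less than 1 year. Former placebo subjects who stop early can. SAP 11.2 does not list its exposure categories; this supposes yearly bands like those in SAP 9.12.

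**How many have a pre-treatment baseline.** ARC003 placebo subjects received AR101 in ARC004, so among the studies with stated allocation the naive entrants come from three:

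- ARC007: 506/3 ≈ 169
- ARC010: 175/4 ≈ 44
- ARC005: 132/3 = 44

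The unrounded sum is about 256. If all of them roll over and 950 subjects enrol, that is 256/950 ≈ 27% naive and 73% experienced.

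**Effect on a pooled mean, illustration only.** Suppose every subject has the same total change, a fraction f of it occurs before an on-treatment baseline, and a share w has such a baseline. The pooled mean then shows 1 − wf of the change since first AR101. With w = 0.73:

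| f | 1 − wf |
|---|---|
| 0.25 | 0.82 |
| 0.50 | 0.64 |
| 0.75 | 0.45 |

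The documents give no value for f.

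**Immunoglobulins.** Two layouts fit the text of SAP 11.1. If the change summary follows the 1-3, 4 and 5 split, Pathways 4 and 5 stay unmixed and the mixing is Pathways 1 and 2 with Pathway 3. If it follows the pooled default, all five are mixed.

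**The case against.** The best defence is that change during ARC008 is a legitimate quantity for an extension study and matches the anchor used for Study Day and treatment-emergent events. Nothing is tested. Observed SPT values by visit, and immunoglobulin levels by time point and total exposure, do not depend on any baseline definition. SAP 8.3 tabulates baseline values by pathway, and listings show each subject. All of this stands and limits the damage. It does not explain why change since ARC008 entry should be arranged by exposure that began earlier, or why naive and treated baselines should share one mean.

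It is also fair that SPT pooling comes from a general rule and that the table shells are not available. Section 11.2 nevertheless names no exception, and SAP 6.3 lists none for SPT.

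Three stronger readings are tempting, and the documents do not support them:

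- A reader might infer that immunoglobulin change is also tabulated by total exposure. Section 11.1 says so only for the by-time-point statistics.
- A reader might quote a definite attenuation. Any percentage rests on an assumed f.
- A reader might say the exploratory objective will be answered by a biased estimate. The plan declares no target of change since first AR101, and other outputs bear on the objective. The supportable criticism concerns labelling and interpretation.

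**Conclusion.** The point holds in full for SPT, given the default pooling. The change covers less treated time than its label for AR101-experienced subjects: about 2 of 3 years in Pathway 4, and about 1.9 to 3.6 of 5 years after AR101 in ARC003 and ARC004. The latter range depends on the assumed 22 to 52 weeks of ARC003 up-dosing and on reaching 5 years in total.

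For immunoglobulins the finding is narrower. The layout of the change summary is unspecified, and naive and experienced subjects are mixed under either available reading. The size of any distortion in the means cannot be derived from the documents. Because the endpoints are exploratory and descriptive, the consequence is a table that is easy to misread; no error rate or power is affected.

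**What to change.** 1. Present SPT and immunoglobulin change from baseline separately for AR101-naive (Pathways 3 and 5) and AR101-experienced (Pathways 1, 2 and 4) subjects. For immunoglobulins, split Pathway 3 from Pathways 1-2 and keep Pathways 4 and 5 apart. State in SAP 11.1 whether the change summary is stratified by exposure.
2. Label the quantity as change since ARC008 entry. This is still needed within the experienced column, where prior exposure varies.
3. Where pre-AR101 values exist in the originating study (ARC001, ARC003, ARC005, ARC007 or ARC010), add a supplementary change from the last value before the first-ever AR101 dose to the exposure-stratified tables.

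Steps 1 and 2 use data already held. They cost some programming and give smaller cells per column. Step 3 needs earlier-study laboratory and SPT data, in some cases from two studies back. The documents do not confirm that these exist in comparable form, and some subjects may lack a value, so step 3 should supplement the planned baseline and not replace it. SAP version 2 was written after database lock with changes confined to Appendix A, so anything added after lock should be labelled post hoc, as SAP 6.1 provides.
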